We also intend to follow children into the school system with permission to access NPD data at a later stage. To do this, we would need to obtain signed parental consent so that the Local Authorities can share information on school destination using existing information from the project, including child name, date of birth and home postcode. We plan to include in the Memorandum of Understanding and the Data Sharing Agreement with Local Authorities agreement to provide details on child's school destination in February 2021 and February 2022. These two data collection points reflect the expectation that the recruited cohort will enter school in either September 2021 or September 2022 (depending on age at, and month of, recruitment). Allocation of school places is generally conducted prior to February in the preceding academic year. Analysis of NPD data will be conducted as part of a longer term follow up done in addition to the present evaluation. It is anticipated that the focus will be on the Reception Baseline Assessment, which measures communication, language, literacy skills and maths, to assess school readiness and emergent literacy skills. A longer term follow-up is also anticipated. Given that the KS1 assessments will become optional in 2023 (the year our older cohort of children will enter Year 2) and that the phonics assessment administered in Year 1 only measures one discreet aspect of the skills needed in learning to read we anticipate this being the Early Years Foundation Stage profile, focusing on communication and language, personal, social and emotional development, and literacy attainment.

Analysis plan

The statistical analysis will follow the most recent EEF guidance, and will be described in detail in a Statistical Analysis Plan (SAP) prepared within three months of the last participant being randomised. All analyses will be conducted following intention-to-treat (ITT) principles, using two-sided statistical tests at the 5% significance level. This means that participants will be

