analysed according to the group they were assigned to (either intervention or control) regardless of adherence to that condition or not (i.e. participants allocated to receive the intervention will be analysed within the intervention group even if they do not participate in the programme). Where participants withdraw from the programme this shall not be classed as withdrawal from the study and participants will be asked to continue participating in the data collection and data processing aspects of the study. Baseline data will be summarised descriptively, both as randomised and as included in the primary analysis, with no formal comparisons being undertaken. Both adjusted and unadjusted summaries of the outcome measures will be presented, with p-values and appropriate 95% confidence intervals (CI) given for all between group comparisons.

A CONSORT diagram will be produced to show the flow of households and participants through the trial.

Primary Analysis

Linear regression will be used to compare raw BPVS-III scores between the two groups. Group allocation, baseline (raw) BPVS-III score, age and Local Authority will be included as fixed effects in the model. Participants with either age missing or baseline BPVS-III score missing will have these imputed with the relevant strata specific mean. Hence all participants with non-missing BPVS-III scores at follow up will be included, as randomised, in the primary analysis model. The BPVS-III is a norm-referenced test and standardised for children aged 3 years to 16 years and 11 months. However the children being recruited as part of this trial will all be less than three years old at baseline, meaning no age standardised scores exist. Hence the inclusion of age as a covariate. The inclusion of age as a covariate is also likely to increase the precision of the estimate of the treatment effect. Inferences regarding the effectiveness of the ParentChild+ programme will be based on the adjusted difference in mean score between the two groups suggested by this model. Effect size will be summarised using Hedges' g and associated 95% CI.

Further analyses of primary outcome

Further analyses of the primary outcome will be conducted to investigate the possible influence of non-compliance on the result of the primary analysis, and to assess the sensitivity of the primary analysis to variation in the missing data assumptions.

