The responses to the 16 items of the Home Learning Environment Index will be combined to give an overall score, with higher scores being indicative of a more positive home learning environment. This score will be analysed using a linear regression model adjusting for allocation, baseline score and local authority. Any missing baseline scores will be imputed with the strata specific mean prior to analysis. Hence all participants with a non-missing Home Learning Environment Index score at follow up will be included in the model.

Subgroup Analyses

Three pre-specified exploratory analyses of the primary outcome will be conducted to investigate the possibility of treatment effect heterogeneity among trial participants. Variation in treatment effect will be explored across different levels of the following three baseline characteristics; Children in Need status, (a binary classification of whether or not the child has ever been a “Child in Need” at any time in their life up until baseline), English as an Additional Language (again a binary classification) and baseline score on the ASQ communication subscale. Baseline score for the ASQ will be used for this subgroup analysis because, unlike the BPVS-III, it is age standardised for children as young as 1 month, and therefore appropriate for the developmental stage of participating children at baseline. The communication subscale will be used as it aligns more closely with the construct measured by the BPVS-III than either of the other two ASQ scales that are being collected.

In all three cases treatment effect heterogeneity will be investigated by examining whether or not the inclusion of the main effect (if not already present), and its interaction with randomised group, in the model used for the primary analysis leads to a significant improvement in model fit. If the inclusion of such interactions does lead to improved model fit, then this model will be used to assess between group differences within strata and provide associated inference.

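### As worded, the exploratory subgroup rule is a joint test of main effect and interaction, so a variable that is only prognostic can trigger within-stratum treatment comparisons

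*Protocol*

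**What the plan says.** The Primary Analysis section of the protocol lists the terms of the primary model: "Group allocation, baseline (raw) BPVS-III score, age and Local Authority will be included as fixed effects in the model". Child in Need status, English as an Additional Language (EAL) and baseline ASQ communication are not among them.

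The Subgroup Analyses section plans three pre-specified exploratory analyses of the primary outcome "to investigate the possibility of treatment effect heterogeneity among trial participants". Child in Need status is binary; the other two variables are "English as an Additional Language (again a binary classification) and baseline score on the ASQ communication subscale". For each, the step examined is "the inclusion of the main effect (if not already present), and its interaction with randomised group, in the model used for the primary analysis", and the criterion is that this step "leads to a significant improvement in model fit".

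The consequence comes in the next sentence: "If the inclusion of such interactions does lead to improved model fit, then this model will be used to assess between group differences within strata", with inference attached. The Analysis plan sets the general testing rule: "using two-sided statistical tests at the 5% significance level".

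**The concern.** The stated reference model is the primary model, and for all three variables the main effect is absent from it. The comparison therefore adds a main effect and an interaction together and applies one fit criterion to both. Such a test responds to either term. If the variable merely predicts follow-up BPVS-III after adjustment for baseline score, age and Local Authority, fit improves although the programme works equally well at every level of the variable.

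Residual prognostic value is plausible here. The protocol chooses the ASQ communication subscale because "it aligns more closely with the construct measured by the BPVS-III than either of the other two ASQ scales", and EAL status is plausibly related to a test of English receptive vocabulary. What is at stake is the reading of the subgroup results: a positive fit test opens treatment comparisons by EAL status, Child in Need status or baseline communication, and that test may say nothing about effect modification.

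**Working it through.** **Inputs from the protocol.** Analysed n = 256 (320 less 20%), 1:1 allocation, baseline to follow-up correlation 0.7, two-sided alpha 0.05, power 80%, MDES 0.25 (Sample size calculations); the primary model terms (Primary Analysis); the terms added and the criterion (Subgroup Analyses).

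**Assumed, because the protocol gives no figure.** The prevalence of each binary variable and the residual prognostic effect of each variable. Ranges are shown.

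**1. The plan's own figure.** MDES = (1.960 + 0.842) × √(1 − 0.7²) × √(2/128) = 2.802 × 0.714 × 0.125 = 0.250. It reproduces; power at 0.25 is 79.97%. The sample size is not in question.

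**2. Degrees of freedom.** The primary model has 7 parameters: intercept, group, baseline BPVS-III, age and three for Local Authority. Adding the subgroup main effect and its interaction makes 9. The test as worded is an F test on 2 and 256 − 9 = 247 df.

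**3. False-trigger rate with a true interaction of zero.** Let b be the prognostic effect in residual-SD units (a difference for a binary variable, a slope per SD for a score), and let the variable be independent of the other covariates. The non-centrality is n·b²·p(1 − p) for a binary variable of prevalence p, and n·b² for a standardised score. Examples:

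- p = 0.3, b = 0.2: 256 × 0.04 × 0.21 = 2.15, rejection 24%.
- p = 0.1, b = 0.5: 256 × 0.25 × 0.09 = 5.76, rejection 56%.
- score, b = 0.2: 256 × 0.04 = 10.24, rejection 82%.

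| Variable | b = 0 | b = 0.1 | b = 0.2 | b = 0.3 | b = 0.5 |
|---|---|---|---|---|---|
| Binary, 10% prevalence | 5% | 7% | 13% | 23% | 56% |
| Binary, 20% prevalence | 5% | 8% | 19% | 38% | 82% |
| Binary, 30% prevalence | 5% | 9% | 24% | 49% | 91% |
| Continuous score | 5% | 28% | 82% | 99% | over 99% |

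**4. Simulation check.** With 4,000 simulated trials per setting, the joint test rejected in 37.7% at 20% prevalence and b = 0.3 (formula 38.2%), and in 80.6% for a score with b = 0.2 (formula 82.0%). The 1-df test of the interaction, given the main effect, rejected in 4.6% to 5.7% of trials in every setting.

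**5. Units.** Effects in outcome-SD units give higher rates, because the residual SD is √0.51 = 0.714 of the outcome SD. An effect of 0.2 outcome SD is 0.2/0.714 = 0.28 residual SD. At 30% prevalence, effects of 0.2, 0.3 and 0.5 outcome SD give about 43%, 79% and 99.7%. The mechanism is the same; only the scale differs.

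**The case against.** The strongest reply is that the first sentence should not be read alone. The sentence that sets the trigger speaks of including interactions and does not mention main effects; the parenthesis about the main effect may only mean that the marginal term is kept so that the interaction can be interpreted; and the declared purpose is heterogeneity. The authors may well have meant the interaction alone. That is fair as to intent. However, the text names the primary model as the comparator and defines no interaction-only test or reference model containing the main effect. An analyst who follows it literally runs the 2-df test. Because the protocol states the criterion, this is more than detail left to the SAP.

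A second reply is that the rates rest on assumed inputs, and that closeness to the BPVS-III construct does not establish prognostic value once baseline BPVS-III is in the model. This stands. At 5% prevalence and 0.2 residual SD the rate is only about 9%, and with no residual effect it is 5%.

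A reader might also infer that the plan will declare heterogeneity whenever a variable is prognostic. The protocol does not say so. A significant fit leads to within-stratum estimates from a model that contains the interaction; with a true interaction of zero those estimates would usually be similar, and a false claim would need a further misreading. A charge of selective reporting is likewise unsupported: all three analyses are pre-specified and nothing says that test results or interaction estimates will be withheld.

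**Conclusion.** The point holds as a fault in a stated rule. As worded, the criterion does not separate prognosis from effect modification, and this applies to all three subgroup variables. A purely prognostic variable can, and often would, trigger within-stratum comparisons. How often depends on prevalence and on residual prognostic strength after adjustment, neither of which the protocol gives: from 5% with no residual effect to over 99% for a strongly prognostic score. The calculations also assume 256 analysed and independence of the subgroup variable from the other covariates.

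This should be fixed, but it does not threaten the trial's main conclusion. The subgroup analyses are labelled exploratory, inference on effectiveness rests on the primary model alone, and the sample size is untouched.

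**What to change.** State in the Subgroup Analyses section, or in the SAP before analysis, that the subgroup main effect is in both models being compared and that heterogeneity is judged by the interaction term alone: primary model plus main effect, against primary model plus main effect plus interaction, 1 df for each variable. State also that the interaction estimate and its 95% CI will be reported for all three variables, whatever the p-value. This takes about one sentence and has no cost in data, sample size or resources.

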Sample size calculations were conducted using Stata v15.0. Although the unit of randomisation will be households, in the vast majority of these there will be only one eligible child. Therefore the sample size has been conducted as for an individually randomised trial. Multiple eligible children within a household will be allowed to take part, and in these cases we will use the mean of the scores obtained within the household for statistical analyses. The DT have estimated that they would have capacity to support 160 families in the intervention (40 in each of 4 geographical regions). Using equal randomisation, we aim to recruit 320 families. Assuming scores obtained at baseline and follow up are approximately bivariate normal with a correlation of 0.7 and 20% attrition at follow up (n=64), this sample size (n=256) gives a minimum detectable effect size (MDES) of 0.25 in a two-sided test of the difference between groups adjusted for baseline with nominal type 1 and 2 error rates of 5% (i.e. alpha of 0.05) and 20% (i.e. power of 80%), respectively. This would mean that this study would be able to detect lower effect sizes than those in the US studies discussed above.

Outcome measures

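### Subgroup effects are estimated only after a significant fit test, so they are absent after a negative test and selected on significance after a positive one

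*Protocol*

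**What the plan says.** The Subgroup Analyses section of the Protocol announces: "Three pre-specified exploratory analyses of the primary outcome will be conducted to investigate the possibility of treatment effect heterogeneity". The moderators are Child in Need status (binary), English as an Additional Language (EAL, binary) and the baseline score on the ASQ communication subscale.

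For each, the check is whether the "inclusion of the main effect (if not already present), and its interaction with randomised group, in the model used for the primary analysis" significantly improves model fit. The next sentence sets the consequence: "If the inclusion of such interactions does lead to improved model fit, then this model will be used to assess between group differences" within strata, with associated inference. The section does not say what is reported when fit does not improve.

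The model being extended is defined under Primary Analysis: "Group allocation, baseline (raw) BPVS-III score, age and Local Authority will be included as fixed effects in the model". None of the three moderators is in that list.

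The trial is sized for the overall group difference, with a "minimum detectable effect size (MDES) of 0.25" at 256 analysed. The Protocol gives no expected share for either binary subgroup and no expected interaction size.

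**The concern.** The rule makes the reporting of an estimate depend on a p-value, in a trial with little power for interactions. This has two consequences.

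- **Negative test.** The reader gets a test result with no promised estimate or interval, and cannot tell an absence of heterogeneity from a shortage of data.
- **Positive test.** The estimates shown are those that happened to differ enough to pass, so the apparent contrast between subgroups is exaggerated on average.

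The wording also leaves unclear what is tested. Since no moderator is in the primary model, the comparison as written adds main effect and interaction together. Such a test can be significant because the moderator predicts vocabulary, with no difference in treatment effect at all.

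These groups bear on how the programme might be targeted. Under Participants, the Protocol asks Local Authorities that use referral routes to give priority to Child in Need families.

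**Working it through.** **Inputs from the Protocol.** Sample size calculations: 256 analysed (128 per arm), baseline–follow-up correlation 0.7, type 2 error "20% (i.e. power of 80%), respectively". Analysis plan: "using two-sided statistical tests at the 5% significance level".

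**Assumptions not in the Protocol.** Subgroup share p; true interaction d in SD units; overall effect 0.25 SD; for the 2-df reading, a prognostic main effect of 0.3 SD.

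**1. The plan's own figure.** Residual SD = √(1 − 0.7²) = 0.714. MDES = (1.96 + 0.84) × 0.714 × √(1/128 + 1/128) = 0.250. The stated 0.25 is reproduced.

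**2. Precision of an interaction with a binary moderator.** SE = 2 × 0.714 / √(256 × p × (1 − p)). At p = 0.5 this is 1.428/8 = 0.179. At p = 0.2 it is 1.428/6.4 = 0.223. Multiplying by 2.80 gives a minimum detectable interaction of 0.50 and 0.63 SD.

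**3. 1-df interaction test, d = 0.25 SD.** Power is the probability that |z| exceeds 1.96 when z has mean d/SE. The mean size of a significant contrast follows from the same truncated normal distribution. The stratum effects are the overall effect plus (1 − p) times the contrast, and the overall effect minus p times the contrast.

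| Share p | SE | Test positive | Contrast when positive (ratio to 0.25) | Larger stratum: true → reported | Smaller stratum: true → reported |
|---|---|---|---|---|---|
| 0.5 | 0.179 | 29% | 0.46 (1.85) | 0.375 → 0.480 (1.28) | 0.125 → 0.020 (0.16) |
| 0.3 | 0.195 | 25% | 0.50 (1.99) | 0.425 → 0.597 (1.41) | 0.175 → 0.101 (0.58) |
| 0.2 | 0.223 | 20% | 0.56 (2.25) | 0.450 → 0.695 (1.54) | 0.200 → 0.139 (0.69) |

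At a share of 10% the test is positive 13% of the time and the contrast ratio is 2.93.

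**4. Sensitivity to the assumed interaction, shares 10–50%.**

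- d = 0.125: positive 7–11% of the time, contrast ratio 3.5–5.7.
- d = 0.375: positive 24–56%, ratio 1.3–2.0.
- d = 0.5: positive 39–80%, ratio 1.1–1.6.

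**5. The literal 2-df test.** Suppose the moderator has a 0.3 SD main effect and no interaction. The SE of the main effect is 0.714/√(256 × p × (1 − p)), which is 0.0893 at p = 0.5 and 0.1116 at p = 0.2. The noncentrality is (0.3/0.0893)² = 11.3 and (0.3/0.1116)² = 7.2. A 2-df chi-square test at 5% is then significant 86% and 67% of the time. By simulation, 93–94% of those significant results have an interaction p-value of 0.05 or more. With a 0.25 SD interaction added, the test is significant 74–91% of the time and the contrast ratio is only 1.04–1.15.

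**6. Without the condition.** The SEs in step 2 do not change and selection disappears (expected ratio 1.0). The 95% CI half-width for the interaction is 1.96 × SE, or 0.35 SD at p = 0.5 and 0.44 SD at p = 0.2.

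The p(1 − p) formula covers the two binary moderators. It does not apply to ASQ communication, a 0–60 score, so no figure is claimed for that one.

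**The case against.** The analyses are labelled exploratory, and the effectiveness conclusion rests on the primary model. Testing an interaction before interpreting strata is a recognised guard against over-reading subgroups, and an unseen SAP might tabulate the interaction coefficients. All of this limits the seriousness. It does not remove the point, because the condition is a positive choice stated in the Protocol, and exploratory results are the ones that most need unfiltered estimates with intervals.

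Three stronger readings are tempting, and the documents do not support them.

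- **That nothing is reported after a negative test.** The fit test is carried out for all three moderators and is itself a result. What is not promised is an effect estimate or interval.
- **That the subgroup effects come out about twice too large.** A factor near two belongs to the interaction contrast, under a 1-df test and one assumed interaction size. The stratum effects move in opposite directions, one up and one down. On the 2-df reading with a prognostic moderator, the exaggeration largely disappears and the fault becomes a different one.
- **That the rule contradicts the Analysis plan's promise of "appropriate 95% confidence intervals (CI) given for all between group comparisons".** A comparison that is never made needs no interval, so the two passages can stand together.

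**Conclusion.** The point holds as a weakness in a stated reporting rule, and should be corrected. Whether a subgroup estimate appears depends either on an interaction test with low power or, on the literal wording, on a joint test that a moderator can pass through prognosis alone. The text does not settle which, since its reference to such interactions could also support a 1-df test.

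The low power is firm for interactions up to the size of the trial's own detectable effect: 29% or less at 0.25 SD for any binary split. The size of the exaggeration is not firm. It runs from about 1.1 to over 5 as the assumed interaction and share change. The 67–86% for the 2-df reading rests on an assumed 0.3 SD main effect and shares of 20–50%. The primary result is unaffected.

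**What to change.** Replace the conditional sentence, in the Protocol or the SAP, with wording to this effect:

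- Test each interaction alone (1 df) against a model that already contains the moderator's main effect.
- Whatever the p-value, report the interaction coefficient with its 95% CI for all three moderators.
- Report the adjusted group difference with 95% CI at each level of Child in Need status and EAL.
- Keep ASQ communication continuous and report the difference at pre-stated values, for example its quartiles. No cut-points are given, so within strata has no defined meaning for this score at present.
- Label all of these exploratory, and state that a non-significant interaction is not evidence of equal effects.

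The cost is a few lines of text and one results table from models already planned. The drawback is that more exploratory estimates with wide intervals will be shown. The label and the closing statement are there to keep them from being over-read.
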